4.1 General Definitions and Derived Variables

4.1.1 Body Mass Index

Body Mass Index (BMI) = Body weight in kilograms divided by the square of the height in meters.

4.2 Primary Endpoint Definition

Change in cerebral NAD/ATP- α ratio measured by ^{31}P -magnetic resonance spectroscopy (^{31}P -MRS) in the posterior brain (encompassing the occipital, parietooccipital and posterior parts of the temporal cortex). The variables are continuous.

The ***primary analysis*** of the ***primary endpoint*** will be:

- The comparison between the dose stable (DS-group) and dose escalation group (DS-group), in cerebral NAD levels measured by ^{31}P -MRS at week 12 depending on randomization group and adjusted for ^{31}P -MRS at baseline.

The **secondary analyses** of the **primary endpoint** will be:

- The comparison of change over time from baseline to week 4, week 8 and week 12, between the DE-group, PL-group and the DS-group, in cerebral NAD levels measured by ^{31}P -MRS, depending on randomization group, time and their interaction adjusted for random individual intercept.
- The comparison between the dose stable (DS-group) and placebo group (PL-group), in cerebral NAD levels measured by ^{31}P -MRS at week 12 depending on randomization group and adjusted for ^{31}P -MRS at baseline.

4.3 Secondary Endpoint Definition

4.3.1 Determine whether NR-therapy augments NAD levels in the central nervous system (CNS) in a dose-responsive manner, as measured by LC-MS

Change in the cerebrospinal fluid (CSF) levels of NAD or other metabolites of the NAD metabolome*, measured. If NAD is measured directly this will be compared. If NAD is not detected or not measurable, the metabolite reflecting NAD levels, will be used for analysis. The variables are continuous. Metabolites from the NAD metabolome will be measured by liquid chromatography mass spectrometry. The variables are continuous.

The **primary analysis** of the **secondary endpoint** will be:

- The comparison between the dose stable (DS-group) and dose escalation group (DE-group), in NAD or NAD metabolite* levels measured by HPLC-MS at week 12 depending on randomization group and adjusted for NAD or NAD metabolite* at baseline.

The **secondary analysis** of the **secondary endpoint** will be:

- The comparison between the dose stable (DS-group) and placebo group (PL-group), in NAD or NAD metabolite* levels measured by HPLC-MS at week 12 depending on randomization group and adjusted for NAD or NAD metabolite* at baseline.

***The NAD metabolome is comprised of:** Nicotinamide adenine dinucleotide oxidized (NAD $^{+}$), Nicotinamide adenine dinucleotide reduced (NADH), NAD $^{+}$ /NADH ratio, total NAD (sum of NAD $^{+}$ and NADH), Nicotinamide adenine dinucleotide phosphate oxidized (NADP $^{+}$), Nicotinamide adenine dinucleotide phosphate reduced (NADPH), NADP $^{+}$ /NADPH ratio, total NADP (sum of NADP $^{+}$ and NADPH), 1-methyl nicotinamide (Me-Nam), nicotinic acid-adenine dinucleotide (NAAD), N1-methyl-2-pyridone-5-carboxamide (Me-2-PY), Nicotinamide (Nam), Nicotinamide N-oxide (Nam N-oxide), ADP-ribose (ADPR), Nicotinic acid riboside (NAR), Nicotinamide riboside (NR), Nicotinamide mononucleotide (NMN), Nicotinic acid (NA).

4.4 Exploratory Endpoint Definitions

Due to the exploratory nature of the trial these outcomes are subject to change of analysis method. The preliminary plan for analysis is the following:

The following exploratory outcomes were recorded at V1, V2, V3 and V4 and will be analysed using the same methodology as the primary endpoint (see section 4.2):

- Change in the NR-related pattern (NRRP). This is calculated from the FDG-PET scans as described in the imaging protocol section of the trial protocol. The values are continuous variables.
- Change in the AD-related pattern (ADRP). This is calculated from the FDG-PET scans as described in the imaging protocol section of the trial protocol. The values are continuous variables.
- Change in the NAD metabolome in blood and urine as measured by HPLC-MS. These values are continuous variables.
- Change in cognitive symptoms from AD as measured by the ADAS-Cog 13 scale. The values are continuous variables.
- Change in cognitive symptoms measured by CDR-SB. The values are continuous variables.
- Change in cognition as measured by the MoCA scale. Scales will be analysed both as total scores and by subsections. The values are continuous variables.
- Change in cognition as measured by Trail Making Test A and B. Scales will be analysed as total scores. The values are continuous variables.
- Change in ADL in AD, as measured by the IADL and PADL scales. Scales will be analysed both as total scores and by subsections. The values are continuous variables.
- Change in neuropsychiatric symptoms measure with NPI-Q and MADRS. Scales will be analysed as total scores. The values are continuous variables.
- Change in inflammatory markers in blood and/or urine. These values are continuous variables.
- Change in proteostasis, measured by RNA expression analysis of lysosomal and proteasomal pathways. These values are continuous variables.
- Change in gene and protein expression in AD. These values are continuous variables.
- Change in methylation metabolism via decreased availability of methyl-donors such as for example S-adenosyl methionine (SAM). These values are continuous variables.
- Change in methylation metabolism via decreased DNA methylation globally or at specific sites. These values are continuous variables.
- Change in methylation metabolism via decreased DNA methylation globally or at specific sites. These values are continuous variables.
- Change in methylation metabolism via aberrant folate and one-carbon metabolism. These values are continuous variables.

The following exploratory outcomes were recorded at V1 and V4 and will be analysed using the same methodology as the secondary endpoint assessing NAD in CSF (see section 4.3):

- Change in the NAD metabolome in the central nervous system as measured by HPLC-MS. These values are continuous variables.

- Change in inflammatory markers in the central nervous system. These values are continuous variables.
- Change in methylation metabolism via decreased synthesis of neurotransmitters like dopamine and serotonin. These values are continuous variables.
- Change in gut microbiome composition as measured by microbial DNA analysis of faeces. These values are continuous variables.

4.5 Overview of Endpoints

Endpoint level	Analysis level	Endpoint	Timeframe	Type
Primary Endpoint				
	Primary	Cerebral NAD ³¹ P-MRS: Difference between DE-group and DS-group.	84 ± 7 Days	Continuous
	Secondary	Cerebral NAD ³¹ P-MRS: Difference between DE-group-, DS-group, and PL-group.	84 ± 7 Days	Continuous
	Secondary	Cerebral NAD ³¹ P-MRS: Difference between DS-group and PL-group.	84 ± 7 Days	Continuous
Secondary Endpoint				
	Secondary	NAD levels in CSF: Difference between DE-group and DS-group.	84 ± 7 Days	Continuous
	Secondary	NAD levels in CSF: Difference between DS-group and PL-group.	84 ± 7 Days	Continuous
Exploratory Endpoints (see section 4.4)				
Safety				
	N/A	Number and severity of adverse events between treatment groups and study visits.	During trial	Continuous

5 Analysis Methods

5.1 Methods for Primary Endpoint

5.1.1 Descriptive Statistics

Cerebral NAD measured by ^{31}P -MRS will be summarized by group for visits V1, V2, V3 and V4 using descriptive statistics (N, mean, standard deviation). Descriptive statistics will be based on non-imputed data. Data will be presented both in tabular and graphical format.

5.1.2 Primary Inferential Analysis

The ***primary analysis*** of the ***primary endpoint*** will be performed using analysis of covariance (ANCOVA) between the dose stable (DS-group) and dose escalation group (DE-group), i.e. the regression of NAD levels measured by ^{31}P -MRS at week 12 depending on randomization group and adjusted for ^{31}P -MRS at baseline. No additional adjustments/covariates will be used. As this is the single primary outcome, alpha will be set at 0.05. No correction for multiple testing will be performed.

The formula for this calculation in R is:

```
lm_object = lm(NAD_at_V4 ~ Group + NAD_at_V1)
```

5.1.3 Effect Estimates

The primary effect estimate will be the B-coefficient with confidence intervals and Cohen's d. Cohen's d will be calculated as the difference in the means between two groups and divided by the pooled standard deviation.

The Beta coefficient will be calculated in R in the following manner:

```
Beta_coefficient = summary(lm_object)$coefficients
```

Confidence intervals will be calculated in R in the following manner:

```
Confidence_intervals = confint(lm_object)
```

P-values will be retrieved from the summary of the lm_object:

```
P_values = summary(lm_object)$coefficients
```

5.1.4 Assumption Checks and Alternative Analyses

Assumptions for ANCOVA will be tested in the following manner:

Normal distribution of residuals: Normality of residuals will be assessed by QQ-plots and the Shapiro-Wilk test.

5.1.5 Missing Data

For the primary outcome, missing data occur if a patient has not completed the study or not completed ^{31}P -MRS imaging within the time window of the final visit 12 weeks \pm 7 days.

As the primary analysis uses two timepoints (V1 and V4), in the case of a participant missing V4 measurements, this patient will not be included in the analysis.

For the secondary analysis of the primary outcome using a linear mixed model (LME, see point 5.1.7), missing data will not be imputed but treated as missing at random.

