## **10.3 Population for Analysis**

Intention to treat (ITT)/Full analysis set (FAS) population: All participants, regardless of protocol adherence.

The Safety Analysis Set (SAS) will include all patients having received at least one study treatment infusion after randomisation.

The Per Protocol Analysis Set (PPS) will include all randomized patients meeting the study eligibility criteria and with no major protocol deviations affecting the treatment efficacy.

The following are pre-defined major protocol deviations regarded to affect the efficacy of the intervention:

- Entering the trial when the eligibility criteria should have prevented trial entry.
- Discontinuation of intervention prior to  $84 \pm 7$  days.
- Received or used other intervention than allocated.
- Adherence to allocated treatment below 80%.
- Visit date interval larger than  $28 \pm 7$  days between individual visits (i.e.: V1 and V2, V2 and V3 and V3 and V4)\*.
- Visit date interval larger than  $84 \pm 7$  days from V1 to V4\*.
- Not fasting before neuroimaging.

\*Due to updated findings from a pharmacokinetic study (ClinicalTrials.gov, NCT: NCT05698771, in revision) that NAD levels increase and reach a plateau within 1-2 weeks of NR treatment both in healthy

individuals and persons with Parkinson's disease. A 3 week period should therefore be sufficient to assess the effects of increasing NR dosage.

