## 10.4 Planned analyses

All statistical analysis is planned after the completion of the study.

All randomized patients will be included in the primary analyses. All randomized patients will be included in the primary analyses and sensitivity analyses will be carried out comparing results from the ITT, SAS and PPS data sets. In the case of missing assessments, the subject will be included if possible.

The *primary analysis* of the primary endpoint will be performed using analysis of covariance (ANCOVA) between the dose stable (DS-group) and dose escalation group (DS-group), i.e. the regression of NAD levels measured by P-MRS at week 12 depending on randomization group and adjusted for P-MRS at baseline. No additional adjustments/covariates will be used. As this is the single primary outcome, alpha will be set at 0.05. No correction for multiple testing will be performed.

The *secondary analysis* of the primary endpoint will be the comparison of change over time from baseline to week 4, week 8 and week 12, between the DE-group and the DS-group. This will be assessed using a linear mixed model (LME), i.e. NAD (P-MRS) at weeks 4,8 and 12 depending on randomization group, time and their interaction adjusted for random individual intercept.

The *primary analysis* of the secondary endpoint will be performed using ANCOVA between the dose stable (DS-group) and dose escalation group (DS-group), i.e. the regression of NAD or NAD metabolite levels measured by HPLC-MS at week 12 depending on randomization group and adjusted for NAD or NAD metabolite at baseline. No additional adjustments/covariates will be used.

The analysis of exploratory endpoints will be performed in a similar manner as for the primary and secondary endpoints. ANCOVA will be used to compare endpoints at week 12, and LME will be used to compare change from baseline to week 4, week 8 and week 12.

In addition, for PET analyses, changes in network scores with treatment will be evaluated for each group separately using permutation tests. Relationships between network values, brain NAD levels and cognitive ratings or between treatment-related changes in these variables will be evaluated using Pearson's product-moment correlations, whereas Spearman rank-order correlation coefficients will be computed for non-normally distributed variables.

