3.4.2 Protocol Deviations

The following are pre-defined major protocol deviations regarded to affect the efficacy of the intervention:

- Entering the trial when the eligibility criteria should have prevented trial entry.
- Discontinuation of intervention prior to 84 ± 7 days.
- Major change in concomitant choline-esterase or memantine treatment.
- Received or used other intervention than allocated.
- Adherence to allocated treatment below 80%.

- Visit date interval larger than 28 ± 7 days between individual visits (i.e.: V1 and V2, V2 and V3, and V3 and V4).
- Visit date interval larger than 84 ± 7 days from V1 to V4.
- Not fasting before neuroimaging with blood glucose > 8

Protocol deviations are classified prior to unblinding of treatment. The number (and percentage) of patients with major and minor protocol deviations will be summarized by treatment group with details of type of deviation provided. The patients that are included in the FAS analysis data set (see point 3.5 below) will be used as the denominator to calculate the percentages. No formal statistical testing will be undertaken.

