5.2.5 Missing Data

For the primary outcome, missing data occur if a patient has not completed the study or CSF collection has not been successful within the time window of the final visit 12 weeks \pm 7 days.

As the primary analysis uses two timepoints (V1 and V4), in the case of a participant missing V4 measurements, this patient will not be included in the analysis.

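### SAP 5.1.5 and 5.2.5 count an obtained week-12 scan or CSF sample as missing when it falls outside ±7 days, so the full analysis set loses observed outcomes that the protocol's ITT definition keeps

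*SAP*

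**What the plan says.** **Missing-data rule.** For the primary outcome, SAP 5.1.5 states that "missing data occur if a patient has not completed the study or not completed" 31P-MRS "imaging within the time window of the final visit 12 weeks" ± 7 days. The consequence follows: "in the case of a participant missing V4 measurements, this patient will not be included in the analysis". SAP 5.2.5 repeats the rule for CSF where "collection has not been successful within the time window of the final visit 12 weeks" ± 7 days.

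**Analysis sets.** Protocol 10.3 defines the ITT/FAS as "All participants, regardless of protocol adherence". Protocol 10.4 adds "All randomized patients will be included in the primary analyses" and "In the case of missing assessments, the subject will be included if possible". The FAS in SAP 3.5 requires randomisation and attendance at baseline, with no condition on visit timing.

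**Where the limit otherwise appears.** SAP 3.4.2 lists "Visit date interval larger than 84 ± 7 days from V1 to V4" among the major deviations, and SAP 3.5 excludes major deviations from the PPS. Protocol 10.3 does the same.

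**Sensitivity analysis.** SAP 5.1.6 and 5.2.6 compare the FAS with the PPS and plan nothing else.

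**Other V4 windows.** SAP 2.4 sets the V4 time point for analysis and tabulation at days 81 to 87. It also calls a visit a major deviation only when it is more than 7 days beyond a ± 72-hour window. SAP 4.5 gives the endpoint a timeframe of 84 ± 7 days.

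**The concern.** A patient scanned at baseline and again on day 92 has both values the ANCOVA needs. Under SAP 5.1.5 that patient is removed, for a timing deviation of the kind that the protocol's ITT definition disregards.

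Three things are at stake:

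- **Information.** Observed values are lost from a contrast that rests on 20 DS patients.
- **Protection of randomisation.** If V4 is delayed for reasons that differ by arm, the patients removed are a selected group.
- **Detection.** No planned analysis of the primary endpoint uses the discarded scans, so a reader of the results could not tell whether they mattered.

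The point does not concern patients with no V4 scan at all. Leaving them out of a complete-case ANCOVA is a separate question.

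**Working it through.** **1. The rule applied to cases.** 12 weeks ± 7 days is days 77 to 91.

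| V4 scan (visit on the same day unless stated) | Outcome under SAP 5.1.5 | V1–V4 interval under SAP 3.4.2 |
|---|---|---|
| Day 84 | observed | within limit |
| Day 92 | missing, patient dropped | major deviation, out of PPS |
| Visit day 90, scan day 92 | missing, patient dropped | visit interval within limit |

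The third row is possible because Protocol Appendix B allows imaging up to 72 hours either side of the physical examination, while SAP 3.4.2 counts visit dates and SAP 5.1.5 refers to completion of imaging. The two limits are therefore essentially, but not exactly, the same.

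**2. Consequence for SAP 5.1.6.** The missing-data definition is not restricted to one analysis set. An out-of-window scan therefore enters neither the FAS nor the PPS result, and comparing the two cannot show its influence.

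**3. The plan's own sample-size figure.** SAP 5.5 and Protocol 10.1 require 30 in the DE group for 90% power at α = 0.05, raised to 40 for drop-out and a safety margin. No SD and no DS-arm requirement are given, so the 30 cannot be reproduced. The step to 40 corresponds to an allowance of 25%: 30/(1 − 0.25) = 40.

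**4. Precision.** The documents give no out-of-window rate, so the share lost, f, is an assumption, taken as equal in both arms. The DE–DS standard error is proportional to √(1/n_DE + 1/n_DS), so its inflation is 1/√(1 − f) − 1:

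- f = 5%: 2.6%
- f = 10%: 5.4%
- f = 15%: 8.5%

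Losses in the DS arm cost more. The full-sample variance factor is 1/20 + 1/40 = 0.0750. Losing two DS scans gives 1/18 + 1/40 = 0.0806 (+7.4%). Losing two DE scans gives 1/20 + 1/38 = 0.0763 (+1.8%).

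**5. Power.** This uses a two-sided test at 0.05 and a noncentral t with noncentrality d/√(1/n_DE + 1/n_DS), where d is the difference in residual-SD units. Because the planning effect cannot be recovered, two anchors are shown. The 15 in the second is an assumption taken from the 2:1 allocation.

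| Anchor | d | No loss (40 v 20) | 5% lost | 10% lost | 15% lost |
|---|---|---|---|---|---|
| 90% at 40 v 20 | 0.903 | 90.0% | 88.4% | 86.6% | 84.6% |
| 90% at 30 v 15 | 1.049 | 96.4% | 95.6% | 94.6% | 93.3% |

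Under the second anchor power returns to 90% only when 25% are lost, since 40 × 0.75 = 30 and 20 × 0.75 = 15.

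**6. Bias.** If a share f of one arm's scans is discarded and these differ by g SD from the retained ones, the retained mean is off by f × g SD. For example, f = 10% and g = 0.5 gives 0.05 SD. Neither f nor g is in the documents.

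**The case against.** The strongest reply is that an analysis set says who is analysed, while a window says which measurement counts as the week-12 outcome. SAP 4.5 attaches 84 ± 7 days to the primary endpoint, so SAP 5.1.5 may only be applying the endpoint's own timeframe. This stands in part. A reader might infer that any visit window breaches intention-to-treat, and the documents do not support that, because windowing is ordinary practice. The difficulty here is narrower: the same limit is listed as an adherence deviation for the PPS, the protocol's FAS disregards adherence, and an obtained scan leaves the analysis with nothing in its place. Protocol 10.3's footnote, which says NAD plateaus within 1–2 weeks and that three weeks suffice to assess a dose, gives no reason to regard a slightly late scan as uninformative.

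It is also fair to say that Protocol 10.4 does not mention late scans. Its wording on missing assessments leaves room for patients with no scan, but with both scans in hand inclusion is possible.

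Three further inferences go too far:

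- **That power falls below plan.** This holds only if 90% applies at 40 v 20. The documents place 90% at 30 in the DE group, and the increase to 40 allows for some loss.
- **That delay from intolerance at the top dose biases the result.** Nothing documents this. Protocol 6.4.1 says withdrawn patients are not followed up, so that route would mostly leave no scan.
- **That DE v DS is the trial's smallest comparison.** DS v placebo is smaller, at 20 v 20.

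Finally, patients without a V4 value still contribute earlier visits to the mixed model in SAP 5.1.7. That softens the loss for the secondary analysis but not for the primary one.

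**Conclusion.** The point holds from the text alone: SAP 5.1.5 and 5.2.5 discard obtained V4 values on a timing criterion that otherwise belongs to the PPS, against the FAS as Protocol 10.3 and 10.4 describe it, and the planned sensitivity analysis cannot reveal the effect.

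The size is modest and conditional. For 5 to 15% of scans out of window in both arms, the loss is 1.6 to 5.4 percentage points of power under the less favourable anchor and 0.8 to 3.1 under the other. Both depend on an assumed out-of-window rate and an assumed effect. Arm-dependent bias is a risk, not a finding. The case for change is that the rule is inconsistent, its effect would go unseen, and correcting it is cheap.

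**What to change.** 1. In SAP 5.1.5 and 5.2.5, define missing as no usable V4 scan or CSF sample obtained.
2. Keep every obtained V4 value in the FAS ANCOVA.
3. Apply 84 ± 7 days to the PPS and to an added sensitivity analysis of the FAS restricted to in-window values. State whether the limit runs on the visit date or on the imaging or sampling date.
4. Tabulate, by arm, the day of the V4 scan and whether the patient was on or off study drug at that time.
5. Reconcile the day 81–87 time point in SAP 2.4 and the 84 ± 7 timeframe in SAP 4.5 with this rule. Otherwise a late scan still has no V4 label and the exclusion returns.

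The cost is SAP wording, one extra model fit for each endpoint and one table; no new data are needed beyond scan dates and drug status. The downside is that a few FAS values may come from late scans, some possibly off drug. The in-window and PPS analyses isolate them.

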5.1.6 Sensitivity Analyses

Sensitivity analysis will be performed by comparing the results of analysis with the FAS and PPS populations. If there is a notable difference this will be commented upon.

5.1.7 Secondary Analyses of the Primary Endpoint

The *secondary analyses* of the *primary endpoint* will be:

1. Analysis of covariance (ANCOVA) between the dose stable (DS-group) and placebo group group (PL-group), i.e. the regression of NAD levels measured by ^{31}P -MRS at week 12 depending on randomization group and adjusted for ^{31}P -MRS at baseline. No additional adjustments/covariates will be used. No correction for multiple testing will be performed.

The above-mentioned analysis will be performed in the same manner as the primary analysis for the primary endpoint.

2. Comparison of change over time from baseline to week 4, week 8 and week 12, between the DE-group, DS-group and the PL-group. This will be assessed using a linear mixed model (LME), i.e. NAD (^{31}P -MRS) at weeks 4, 8 and 12 depending on randomization group, time and their interaction adjusted for random individual intercept. The above-mentioned analysis will be performed using a linear mixed model (LME) comparing NAD level as a function of group with time and the interaction between group and time as independent variables. Individual subjects will be random effects.

The following formula will be used in R format:

```
NAD_level ~ Group + Visit + Group * Visit + (1 | Subject)
```

Visit will be treated as a numeric variable if there is no plateau effect. If there is a plateau effect in the data, visit will be treated as a factor.

The primary effect estimate will be the B-coefficient with confidence intervals and Cohen's d. Cohen's d will be calculated as the difference in the means between two groups and divided by the pooled standard deviation.

The dose stable group will be set as the reference to which the dose escalation and placebo groups will be compared.

No additional covariates will be included in the LME model.

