2.3.2 Confidence Intervals and p-values

All calculated p-values will be two-sided and compared to a 5% significance level. If a p-value is less than 0.05, the corresponding treatment group difference will be denoted as statistically significant. All efficacy estimates will be presented with two-sided 95% confidence intervals. As there is only one primary null hypothesis to be tested in this trial, there will be no adjustments for multiplicity.

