5.3 Methods for Continuous Exploratory Endpoints

As described in section 4.4, due to the nature of the exploratory outcomes, the analysis method is subject to change. The preliminary plan is that they will be analysed in the same manner as the primary endpoint if they have observations at V1, V2, V3 and V4 (see sections 5.1.2 and 5.1.7) and the same manner as the secondary endpoint if they only have observations at V1 and V4 (see sections 5.2.2 and 5.2.7).

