5.5 Sample size

Our primary null hypothesis (H_0) is that the NR-induced increases in cerebral NAD levels (measured by ^{31}P -MRS), or NRRP expression (measured by FDG-PET) are not dose-responsive. The alternative hypothesis (H_A) is that at least one of these measures will be dose responsive. In the NADPARK study, all three measures showed a highly significant increase in the group receiving 1000 mg NR ($n = 15$) compared to the placebo group ($n = 15$). In the NADPARK study⁹, treatment with 1000mg of NR led to an increase in cerebral NAD-levels by a factor of 1.27 from baseline in the treatment group, whereas the change in the placebo group was negligible at -0.43%. Under the H_A , we assume that cerebral NAD levels will increase in a linear fashion in the 2000 mg NR and 3000 mg NR groups, respectively. Based on these assumptions and given a type I error rate of 5% ($\alpha = 0.05$) and a type II error rate of 10% ($\beta = 0.1$, power = 90%), we estimated that a sample size of 30 individuals will be required in the dose escalation group. Accounting for drop-out and statistical safety margin, we estimate that the study requires 40 subjects in this group.

For the secondary outcomes, we assume that the metabolomic analyses will have sufficient power, since they produced very large effect sizes and highly significant results in the NADPARK study with 15 individuals per group.

6 Safety Analyses

General safety evaluations will be based on the incidence, intensity, and type of AEs, and clinically significant changes in the patient's physical examination findings, vital signs, and clinical laboratory results. Only AE grade 2 and above will be recorded. Safety variables will be tabulated and presented for all patients in the safety set.

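### The mixed model for the dose-response secondary objective does not use the arms' common baseline mean, and the SAP does not say whether V1 is an outcome row; the cost is precision, mainly at week 8

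*SAP*

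**What the plan says.** - **Primary analysis (SAP 5.1.2).** Week-12 NAD is regressed on group and baseline NAD: "lm_object = lm(NAD_at_V4 ~ Group + NAD_at_V1"). The DS-PL comparison at week 12 (SAP 5.1.7, item 1) has the same form.
- **Mixed model (SAP 5.1.7, item 2).** The formula is "NAD_level ~ Group + Visit + Group * Visit + (1 | Subject"), with DS as the reference arm. The section adds: "No additional covariates will be included in the LME model". Visit is numeric unless the data show a plateau, in which case it becomes a factor.
- **Protocol 10.4** describes the model in the same way, "depending on randomization group, time and their interaction adjusted for random individual intercept". No section of either document adds a baseline term or sets the arms' baseline means equal.
- **Outcome rows.** SAP 5.1.7 speaks both of change from baseline, which makes V1 an outcome row, and of NAD at weeks 4, 8 and 12, which leaves it out.
- **Reach.** SAP 5.3 provisionally carries the method to the exploratory endpoints, which are "analysed in the same manner as the primary endpoint if they have observations at V1, V2, V3 and V4".

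**The concern.** Randomisation makes the true V1 means equal across arms. The primary ANCOVA exploits this; the mixed model does not. Its random intercept describes how a person's visits correlate, but the free Group term still gives each arm its own V1 mean. Chance imbalance at V1 therefore passes into any contrast measured from V1. If V1 is not a row, the baseline measurement is not used at all.

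Two things are at stake. The first is precision for the secondary objective on dose response in cerebral NAD. The effect is greatest at week 8, when DE takes 2000 mg and DS 1000 mg: this is the only DE-DS dose contrast with no separate ANCOVA. The second is consistency: at week 12 the mixed model and the primary ANCOVA can give different DE-DS estimates purely because of baseline imbalance.

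**Working it through.** **Inputs from the documents.** DE 40, DS 20 (SAP 1.2.1). Random intercept, hence one common correlation rho between all visits (SAP 5.1.7). Two-sided 5% level: "All calculated p-values will be two-sided and compared to a 5% significance level" (SAP 2.3.2).

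**Input assumed.** rho is not stated anywhere, so a range of 0.3 to 0.9 is shown.

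**The plan's own figure.** SAP 5.5 says "we estimated that a sample size of 30 individuals will be required in the dose escalation group", later raised to 40. It gives no standard deviation, so this cannot be recomputed, and neither document gives a precision or power figure for the mixed model. The comparison below is therefore relative. Variances of the DE-DS contrast are in units of sigma^2 (1/40 + 1/20) = 0.075 sigma^2, with complete data, by generalised least squares.

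**Reading A: V1 is an outcome row, Visit a factor**

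- Planned contrast (change-score difference): 2(1 - rho).
- With a common V1 mean, or V1 as covariate: 1 - rho^2.
- Ratio: (1 + rho)/2. Precision loss: 1 - (1 + rho)/2 = (1 - rho)/2.

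| rho | Planned | Adjusted | Loss | Increase in SE |
|---|---|---|---|---|
| 0.3 | 1.40 | 0.91 | 35% | 24% |
| 0.5 | 1.00 | 0.75 | 25% | 15.5% |
| 0.7 | 0.60 | 0.51 | 15% | 8.5% |
| 0.9 | 0.20 | 0.19 | 5% | 2.6% |

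Under a common rho these values are the same at week 8 and week 12. As an illustration, an effect that gives the planned contrast 80% power (noncentral t, 57 df) would give the adjusted one 94%, 90% and 86% at rho 0.3, 0.5 and 0.7. The 80% starting point is a convenience, not a figure from the plan.

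**Reading A: Visit numeric (the SAP default)**

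The contrast is now a difference in slopes over four visits, scaled here to 12 weeks. At rho 0.5 its variance is 0.90 as planned and 0.662 with a common V1 mean: a loss of 1 - 0.662/0.90 = 26%. Against the single-visit week-12 ANCOVA (0.75) the planned slope loses 1 - 0.75/0.90 = 17%.

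**Reading B: V1 excluded, Visit a factor**

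- Group difference at one visit: 1 as planned, 1 - rho^2 with V1 as covariate. Loss rho^2: 9% at 0.3, 25% at 0.5, 49% at 0.7.
- Group x Visit coefficient (change from V2): 2(1 - rho) with or without baseline adjustment, that is 1.40, 1.00 and 0.60 at rho 0.3, 0.5 and 0.7. V1 has the same covariance with V2 as with V4, so it is uncorrelated with their difference. Loss: zero.

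**The case against.** **Stands: the size rests on an assumed rho.** With V1 as a row, the loss falls as rho rises, to 10% at 0.8 and 5% at 0.9. At 0.9 the planned numeric slope is even slightly less variable than the week-12 ANCOVA (0.18 against 0.19), though a common V1 mean still improves on it (0.172).

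**Stands: a quarter is not lost on every reading.** A reader might infer this because (1 - rho)/2 and rho^2 are both 25% at rho 0.5. The second expression applies only to per-visit group differences. The reported interaction coefficient gains nothing when V1 is excluded; its fault there is that it measures change from V2, not from baseline.

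**Stands: weeks 4 and 8 are not equally affected.** Protocol 5.2 puts DE and DS on the same 1000 mg per day up to week 4, so the week-4 DE-DS contrast carries no dose difference. Week 12 has baseline-adjusted ANCOVAs for DE-DS and DS-PL.

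**Stands: validity is not threatened.** Baseline imbalance could be taken to bias the mixed model, but under randomisation its contrasts are unbiased. SAP 2.3.1 names one primary analysis, so there is a hierarchy if the two models disagree. SAP 4.4 and 5.3 leave the exploratory methods open to change.

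**Does not stand: that the random intercept already adjusts for baseline.** With a free Group effect, factor Visit and complete data, the V1-to-V4 interaction equals the change-score difference exactly.

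**Conclusion.** The point holds as one of precision and consistency in a secondary analysis. With V1 as an outcome row, the planned DE-DS contrasts give up (1 - rho)/2 of their precision under factor Visit, and about 26% in the slope at rho 0.5 under the default numeric Visit. With V1 excluded, per-visit differences give up rho^2, and the interaction coefficient does not address change from baseline.

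These figures assume complete data and the SAP's own random-intercept structure; rho is unknown. The documents do not support a claim of bias, of harm to the primary analysis, or of a fixed 25% loss. With only 20 participants in DS and almost no cost to the remedy, the change is worth making before unblinding.

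**What to change.** **Preferred.** State in SAP 5.1.7 that V1 is an outcome row and that all arms share one V1 mean.

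- Factor Visit: remove the Group main effect and let Group enter only through indicators for V2, V3 and V4. Build these indicators explicitly. In R, merely deleting Group and keeping a Group-by-factor-Visit term restores a group difference at V1 and leaves the model unchanged.
- Numeric Visit: code V1 as 0 and keep only Visit and Group x Visit. With any other coding the arms would be constrained to meet at a time other than baseline.

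**Alternative.** Model V2 to V4 with baseline NAD and its interaction with Visit as covariates, and report the group difference at each visit instead of the raw interaction coefficient.

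Either way, amend the sentence that bars covariates so that it agrees with the model, report DE-DS and DS-PL by visit, and use the same form for the exploratory endpoints measured at V1 to V4.

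**Cost.** One model line and a sentence or two of SAP text. There is no new data, visit or participant, and no change to the primary ANCOVA. The preferred form keeps every V1-V4 observation and the missing-at-random handling in SAP 5.1.5.
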